Bilirubin Direct Bilirubin ¹³ , High > 28 days of age	NA	NA	> ULN with other signs and symptoms of hepatotoxicity	> ULN with life-threatening consequences (e.g., signs and symptoms of liver failure)
Total Bilirubin, High > 28 days of age	1.1 to < 1.6 x ULN	1.6 to < 2.6 x ULN	2.6 to < 5.0 x ULN	\geq 5.0 x ULN
Calcium, High (mg/dL; mmol/L) \geq 7 days of age	10.6 to < 11.5 2.65 to < 2.88	11.5 to < 12.5 2.88 to < 3.13	12.5 to < 13.5 3.13 to < 3.38	\geq 13.5 \geq 3.38
Calcium (Ionized), High (mg/dL; mmol/L)	> ULN to < 6.0 > ULN to < 1.5	6.0 to < 6.4 1.5 to < 1.6	6.4 to < 7.2 1.6 to < 1.8	\geq 7.2 \geq 1.8

Parameter	Grade 1 Mild	Grade 2 Moderate	Grade 3 Severe	Grade 4 Potentially life-threatening
Calcium, Low (mg/dL; mmol/L) ≥ 7 days of age	7.8 to < 8.4 1.95 to < 2.10	7.0 to < 7.8 1.75 to < 1.95	6.1 to < 7.0 1.53 to < 1.75	< 6.1 < 1.53
Calcium (Ionized), Low (mg/dL; mmol/L)	< LLN to 4.0 < LLN to 1.0	3.6 to < 4.0 0.9 to < 1.0	3.2 to < 3.6 0.8 to < 0.9	< 3.2 < 0.8
Cardiac Troponin I, High	NA	NA	NA	Levels consistent with myocardial infarction or unstable angina as defined by the local laboratory
Creatine Kinase, High	3 to < 6 x ULN	6 to < 10x ULN	10 to < 20 x ULN	≥ 20 x ULN
Creatinine, High **Report only one	1.1 to 1.3 x ULN	> 1.3 to 1.8 x ULN OR Increase to 1.3 to < 1.5 x participant's baseline	> 1.8 to < 3.5 x ULN OR Increase to 1.5 to < 2.0 x participant's baseline	≥ 3.5 x ULN OR Increase of ≥ 2.0 x participant's baseline
Creatinine Clearance ¹⁴ or eGFR, Low ¹⁴**Report only one	NA	< 90 to 60 ml/min or ml/min/1.73 m ² OR 10 to < 30% decrease from participant's baseline	< 60 to 30 ml/min or ml/min/1.73 m ² OR 30 to < 50% decrease from participant's baseline	< 30 ml/min or ml/min/1.73 m ² OR ≥ 50% decrease from participant's baseline or dialysis needed
Glucose (mg/dL; mmol/L) Fasting, High Nonfasting, High	110 to 125 6.11 to < 6.95 116 to 160 6.44 to < 8.89	> 125 to 250 6.95 to < 13.89 > 160 to 250 8.89 to < 13.89	> 250 to 500 13.89 to < 27.75 > 250 to 500 13.89 to < 27.75	≥ 500 ≥ 27.75 ≥ 500 ≥ 27.75
Glucose, Low (mg/dL; mmol/L) ≥ 1 month of age	55 to 64 3.05 to < 3.55	40 to < 55 2.22 to < 3.05	30 to < 40 1.67 to < 2.22	< 30 < 1.67
Lactate, High	ULN to < 2.0 x ULN without acidosis	≥ 2.0 x ULN without acidosis	Increased lactate with pH < 7.3 without life-threatening consequences	Increased lactate with pH < 7.3 with life-threatening consequences
Lipase, High	1.1 to < 1.5 x ULN	1.5 to < 3.0 x ULN	3.0 to < 5.0 x ULN	≥ 5.0 x ULN
Lipid Disorders (mg/dL; mmol/L) Cholesterol, Fasting, High ≥ 18 years of age	200 to < 240 5.18 to < 6.19	240 to < 300 6.19 to < 7.77	≥ 300 ≥ 7.77	NA

Parameter	Grade 1 Mild	Grade 2 Moderate	Grade 3 Severe	Grade 4 Potentially life-threatening
LDL, Fasting, High ≥ 18 years of age	130 to < 160 3.37 to < 4.12	160 to < 190 4.12 to < 4.90	≥ 190 ≥ 4.90	NA
Triglycerides, Fasting, High	150 to 300 1.71 to 3.42	>300 to 500 >3.42 to 5.7	>500 to < 1,000 >5.7 to 11.4	> 1,000 > 11.4
Magnesium ¹⁵ , Low (mEq/L; mmol/L)	1.2 to < 1.4 0.60 to < 0.70	0.9 to < 1.2 0.45 to < 0.60	0.6 to < 0.9 0.30 to < 0.45	< 0.6 < 0.30
Phosphate, Low (mg/dL; mmol/L) > 14 years of age	2.0 to < LLN 0.65 to < LLN	1.4 to < 2.0 0.45 to < 0.65	1.0 to < 1.4 0.32 to < 0.45	< 1.0 < 0.32
Potassium, High (mEq/L; mmol/L)	5.6 to < 6.0 5.6 to < 6.0	6.0 to < 6.5 6.0 to < 6.5	6.5 to < 7.0 6.5 to < 7.0	≥ 7.0 ≥ 7.0
Potassium, Low (mEq/L; mmol/L)	3.0 to < 3.4 3.0 to < 3.4	2.5 to < 3.0 2.5 to < 3.0	2.0 to < 2.5 2.0 to < 2.5	< 2.0 < 2.0
Sodium, High (mEq/L; mmol/L)	146 to < 150 146 to < 150	150 to < 154 150 to < 154	154 to < 160 154 to < 160	≥ 160 ≥ 160
Sodium, Low (mEq/L; mmol/L)	130 to < 135 130 to < 135	125 to < 130 125 to < 130	121 to < 125 121 to < 125	≤ 120 ≤ 120
Uric Acid, High (mg/dL; mmol/L)	7.5 to < 10.0 0.45 to < 0.59	10.0 to < 12.0 0.59 to < 0.71	12.0 to < 15.0 0.71 to < 0.89	≥ 15.0 ≥ 0.89
HEMATOLOGY				
Absolute CD4+ Count, Low (cell/mm ³ ; cells/L) > 5 years of age (not HIV infected)	300 to < 400 300 to < 400	200 to < 300 200 to < 300	100 to < 200 100 to < 200	< 100 < 100
Absolute Lymphocyte Count, Low (cell/mm ³ ; cells/L) > 5 years of age (not HIV infected)	600 to < 650 0.600 x 10 ⁹ to < 0.650 x 10 ⁹	500 to < 600 0.500 x 10 ⁹ to < 0.600 x 10 ⁹	350 to < 500 0.350 x 10 ⁹ to < 0.500 x 10 ⁹	< 350 < 0.350 x 10 ⁹
Absolute Neutrophil Count (ANC), Low (cells/mm ³ ; cells/L) > 7 days of age	800 to 1,000 0.800 x 10 ⁹ to 1.000 x 10 ⁹	600 to 799 0.600 x 10 ⁹ to 0.799 x 10 ⁹	400 to 599 0.400 x 10 ⁹ to 0.599 x 10 ⁹	< 400 < 0.400 x 10 ⁹
Fibrinogen, Decreased (mg/dL; g/L)	100 to < 200 1.00 to < 2.00 OR 0.75 to < 1.00 x LLN	75 to < 100 0.75 to < 1.00 OR ≥ 0.50 to < 0.75 x LLN	50 to < 75 0.50 to < 0.75 OR 0.25 to < 0.50 x LLN	< 50 < 0.50 OR < 0.25 x LLN OR Associated with gross bleeding
Hemoglobin ¹⁶ , Low (g/dL; mmol/L) ¹⁷ ≥ 13 years of age (male only)	10.0 to 10.9 6.19 to 6.76	9.0 to < 10.0 5.57 to < 6.19	7.0 to < 9.0 4.34 to < 5.57	< 7.0 < 4.34
≥ 13 years of age (female only)	9.5 to 10.4 5.88 to 6.48	8.5 to < 9.5 5.25 to < 5.88	6.5 to < 8.5 4.03 to < 5.25	< 6.5 < 4.03

Parameter	Grade 1 Mild	Grade 2 Moderate	Grade 3 Severe	Grade 4 Potentially life-threatening
INR, High (not on anticoagulation therapy)	1.1 to < 1.5 x ULN	1.5 to < 2.0 x ULN	2.0 to < 3.0 x ULN	≥ 3.0 x ULN
Methemoglobin (% hemoglobin)	5.0 to < 10.0%	10.0 to < 15.0%	15.0 to < 20.0%	≥ 20.0%
PTT, High (not on anticoagulation therapy)	1.1 to < 1.66 x ULN	1.66 to < 2.33 x ULN	2.33 to < 3.00 x ULN	≥ 3.00 x ULN
Platelets, Decreased (cells/mm ³ ; cells/L)	100,000 to < 125,000 100,000 x 10 ⁹ to < 125,000 x 10 ⁹	50,000 to < 100,000 50,000 x 10 ⁹ to < 100,000 x 10 ⁹	25,000 to < 50,000 25,000 x 10 ⁹ to < 50,000 x 10 ⁹	< 25,000 < 25,000 x 10 ⁹
PT, High (not on anticoagulation therapy)	1.1 to < 1.25 x ULN	1.25 to < 1.50 x ULN	1.50 to < 3.00 x ULN	≥ 3.00 x ULN
WBC, Decreased (cells/mm ³ ; cells/L) > 7 days of age	2,000 to 2,499 2,000 x 10 ⁹ to 2,499 x 10 ⁹	1,500 to 1,999 1,500 x 10 ⁹ to 1,999 x 10 ⁹	1,000 to 1,499 1,000 x 10 ⁹ to 1,499 x 10 ⁹	< 1,000 < 1,000 x 10 ⁹
URINALYSIS				
Glycosuria (random collection tested by dipstick)	Trace to 1+ or ≤ 250 mg	2+ or > 250 to ≤ 500 mg	> 2+ or > 500 mg	NA
Hematuria (not to be reported based on dipstick findings or on blood believed to be of menstrual origin)	6 to < 10 RBCs per high power field	≥ 10 RBCs per high power field	Gross, with or without clots OR With RBC casts OR Intervention indicated	Life-threatening consequences
Proteinuria (random collection tested by dipstick)	1+	2+	3+ or higher	NA

* Reminder: An asymptomatic abnormal laboratory finding without an accompanying AE should not be reported to DAIDS in an expedited time frame unless it meets protocol-specific reporting requirements.

13 Direct bilirubin >1.5 mg/dL in a participant < 28 days of age should be graded as grade 2, if < 10% of the total bilirubin.

** Reminder: Choose the method that selects for the higher grade.

14 Use the applicable formula (ie, Cockcroft-Gault in mL/min or Schwartz, MDRD, CKD-Epi in mL/min/1.73m²). Sites should choose the method defined in their study and when not specified, use the method most relevant to the study population.

15 To convert a magnesium value from mg/dL to mmol/L, laboratories should multiply by 0.4114.

16 Male and female sex are defined as sex at birth. For transgender participants ≥13 years of age who have been on hormone therapy for more than 6 consecutive months, grade hemoglobin based on the gender with which they identify (ie, a transgender female should be graded using the female sex at birth hemoglobin laboratory values).

17 The most commonly used conversion factor to convert g/dL to mmol/L is 0.6206. For grading hemoglobin results obtained by an analytic method with a conversion factor other than 0.6206, the result must be converted to g/dL using appropriate conversion factor for the particular laboratory.

APPENDIX 5. PREGNANCY PRECAUTIONS AND THE DEFINITION OF CHILDBEARING POTENTIAL AND CONTRACEPTIVE REQUIREMENTS

Pregnancy Precautions

The effect of ABI-4334 on pregnancy, including preclinical development and reproductive toxicology, has not been assessed. As such, pregnancy precautions are required and contraceptive requirements for female subjects of childbearing potential are described below.

Definition of Female Subjects of Childbearing Potential

As defined in this protocol, “women of childbearing potential” are female subjects who are physiologically capable of becoming pregnant. Conversely, “women of no childbearing potential” are defined as female subjects meeting any of the following criteria:

- Surgically sterile (ie, through bilateral salpingectomy, bilateral oophorectomy, or hysterectomy) or with medically documented ovarian failure
- Postmenopausal, defined as ≥ 54 years of age with no spontaneous menses for ≥ 12 months without alternative medical condition

If female subject is < 54 years of age with no spontaneous menses for ≥ 12 months without alternative medical condition, then follicle-stimulating hormone (FSH) levels should be consistent with menopause at Screening.

Documentation to determine childbearing potential can come from the site personnel’s review of the subject’s medical records, medical examination, or medical history interview.

Contraceptive Requirements

Note that the drug-drug interaction of ABI-4334 and systemic (oral/injectable/implantable) hormonal contraceptives has not been assessed and so systemic hormonal contraceptives are not considered an effective contraceptive method for female subjects of childbearing potential for the purposes of this study.

Female subjects of childbearing potential must have a negative serum pregnancy test at Screening and Day -1 and a negative urine pregnancy test prior to receiving the first dose of study drug on Day 1. Subjects will be instructed to notify the Investigator if they become pregnant at any time during the study, or if they become pregnant within 28 days of the last dose of study drug. Instructions for reporting pregnancy and pregnancy outcomes are outlined in [Section 9.9](#) of the protocol.

- 1) Female subjects of childbearing potential (defined above) must agree to use two effective contraceptive methods, or complete abstinence for the duration of the study and follow-up.
 - Effective contraceptive methods (two are required):

- o Male OR female condom, but not together due to increased risk of breakage
 - o Intra-uterine device (hormonal or copper IUD)
 - o Diaphragm or cervical cap with spermicide (where locally available).
 - o Vasectomy of male partner at least 6 months prior to the first study drug administration
 - o Bilateral tubal ligation
 - Complete abstinence from heterosexual intercourse of reproductive potential.
 - o Note: Abstinence does not require a second contraceptive method and is an acceptable method of contraception only if it is in line with the subject's preferred and usual lifestyle. Periodic abstinence (eg, calendar, ovulation, symptothermal, post-ovulation methods) and withdrawal are not acceptable methods of contraception.
- 2) Female subjects must avoid egg donation from Screening through at least 28 days after administration of the last dose of study drug. All male subjects that are able to procreate (if their female partner is of childbearing potential) must agree to use two effective contraceptive methods with their female partners, or complete abstinence for the duration of the study and follow-up.
- Please refer to the contraceptive requirements listed above. Note: In the case of female partners of male subjects, systemic hormonal birth control may be utilized.

Male subjects must avoid sperm donation from Screening through at least 90 days after administration of the last dose of study drug.

ABI-4334

Study ABI-4334-101 Original Protocol 16 June 2022

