8.3.5 Clinical Laboratory Assessments

Clinical laboratory tests will be performed at the designated central laboratories at the timepoints indicated in [Appendix 1](#), [Appendix 2](#), and [Appendix 3](#). Should any laboratory parameter require urgent testing to support eligibility determination or immediate medical care of a subject, samples can be collected for local laboratory testing. However, only the results from the central laboratories will be reported in the study database for analysis purposes.

The specific components of the clinical laboratory tests are listed below in [Table 2](#).

Table 2. Clinical Laboratory Tests

Panel	Tests
Chemistry	Glucose, sodium, potassium, chloride, bicarbonate, calcium, blood urea nitrogen, creatinine, creatine kinase, uric acid, total and direct bilirubin, ALT, aspartate aminotransferase (AST), gamma-glutamyl transferase (GGT), alkaline phosphatase, lactate dehydrogenase (LDH), triglycerides, total cholesterol, phosphorous (inorganic), total protein, albumin, amylase, lipase
Hematology	Hemoglobin, hematocrit, red blood cell count, RBC indices (MCV), reticulocyte count, white blood cell count including, lymphocytes, monocytes, neutrophils, eosinophils, basophils, platelet counts
Coagulation	Prothrombin time/INR, aPTT
Urinalysis	pH, specific gravity, protein, glucose, ketones, occult blood
Pregnancy tests for female subjects of childbearing potential	Serum pregnancy test and/or urine dipstick pregnancy test
Drug Screen	Dipstick
Serology	HIV-1 Ab, HIV-2 Ab, HCV Ab, HBcAb IgM, HBsAg Note: For antibody tests, if antibody is positive, reflex to DNA or RNA, as applicable
Alcohol	Urine dipstick or breathalyzer

Panel	Tests
Other	FSH for female subjects < 54 years of age with no spontaneous menses > 12 months

Abbreviations: Ab=antibody; ALT=alanine aminotransferase; aPTT=activated partial thromboplastin time; AST=aspartate aminotransferase; DNA=deoxy nucleic acid; FSH=follicle stimulating hormone; GGT=gamma-glutamyl transferase; HBcAb=antibody to the HBV core protein; HBsAg= hepatitis B surface antigen; HCV=hepatitis C virus; HIV=human immunodeficiency virus; IgM=immunoglobulin M; INR=international normalized ratio; LDH=lactate dehydrogenase; MCV=mean corpuscular volume; RBC=red blood cell; RNA=ribonucleic acid

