5.2.1 Graded Laboratory Values

The criteria specified in the study protocol will be used to grade laboratory results as normal (no grade), mild (Grade 1), moderate (Grade 2), severe (Grade 3) or potentially life threatening (Grade 4). See Appendix 4 of the protocol for detailed DAIDS grading criteria on the relevant laboratory tests. For laboratory tests with criteria for both increased and decreased levels, analyses for each direction (ie, increased, decreased) will be presented separately.

Some lab tests require fasting to be graded (i.e. triglycerides and cholesterol). For those lab tests, Baseline will be defined as the last non-missing fasted evaluation prior to the first dose on Day 1.

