5.2.4 Summaries of Categorical Laboratory Results

For categorical urinalysis parameters, the number and percentage of subjects in each category will be presented by treatment and cohort at each visit.

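### Hematuria Grades 1 and 2 (and Grade 3 by casts) need urine microscopy that the scheduled urinalysis does not list, and a new positive occult blood result enters no subject-level treatment-emergent count

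*Combined protocol and SAP*

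**What the plan says.** **What is measured.** Table 2 in protocol 8.3.5 gives the urinalysis panel as "pH, specific gravity, protein, glucose, ketones, occult blood". It lists no urine microscopy, red cell count or casts. The table specifies reflex testing for positive serology, and the schedule footnotes specify it for a positive urine pregnancy test, but none is specified for urinary blood. The schedules in Appendices 1a, 1b and 2 add no microscopy.

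**How hematuria is graded.** The Appendix 4 row is headed "Hematuria (not to be reported based on dipstick findings or on blood believed to be of menstrual origin". Its grades are:
- Grade 1: "6 to < 10 RBCs per high power field"
- Grade 2: "≥ 10 RBCs per high power field"
- Grade 3: "Gross, with or without clots OR With RBC casts OR Intervention indicated"
- Grade 4: "Life-threatening consequences"

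The neighbouring glycosuria and proteinuria rows are graded by dipstick.

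**How the SAP uses this.** SAP 5.2.1 states: "The criteria specified in the study protocol will be used to grade laboratory results", and points to Appendix 4 for the relevant tests. SAP 5.2.1.1 makes a laboratory abnormality treatment-emergent only if it rises by at least one toxicity grade from Baseline (or, with Baseline missing, reaches at least Grade 1). For urinalysis, SAP 5.2.4 states: "For categorical urinalysis parameters, the number and percentage of subjects in each category will be presented by treatment and cohort at each visit". SAP 5.2 also provides a by-subject urinalysis listing in which out-of-range values are flagged.

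**The concern.** The primary endpoint (protocol 3.2.1) includes the proportion of subjects with abnormal laboratory results, and protocol 10.4.4 promises the incidence of laboratory abnormalities. Both are subject-level quantities. The SAP's tool for them is the treatment-emergent graded table, which needs a grade.

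A subject whose occult blood turns from negative to positive after dosing has no planned route to Grade 1 or 2, so the change cannot enter that table. Adverse event tables are not a dependable substitute, because protocol 9.7 says that out-of-range laboratory values are usually not recorded as AEs unless the investigator finds them clinically significant. What is at stake is whether the report can state, by treatment and cohort, how many subjects had new urinary blood after dosing.

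**Working it through.** No figure in the plan needs reproducing. The check has three parts.

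**1. Each grade against the planned tests**

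| Grade | Criterion | Obtainable from the listed panel? |
|---|---|---|
| 1 | Red cell count per field | No |
| 2 | Red cell count per field | No |
| 3 | Gross blood | Yes, visible in a voided sample |
| 3 | Red cell casts | No, needs microscopy |
| 3 | Intervention indicated | Clinical judgement, no microscopy needed |
| 4 | Life-threatening consequences | Clinical judgement, no microscopy needed |

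Two of the four grades are out of reach from planned samples, together with one of the three routes to Grade 3. This does not depend on the urinalysis method, which Table 2 does not name: whatever the method, no cell count or cast result is listed.

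**2. Where a new positive occult blood result appears**

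- Treatment-emergent graded table (SAP 5.2.1.1 and 5.2.1.2): no, because there is no grade to increase.
- Urinalysis category table (SAP 5.2.4): yes, as a count of subjects at that visit.
- By-subject listing (SAP 5.2): yes, flagged if out of range.
- Any count per subject across visits, worst post-Baseline category or shift from Baseline: none planned.

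A visit-by-visit table does not give the subject-level figure. As an illustration, take 6 active subjects in a Part A cohort with one positive at each of Days 2, 3 and 7. The same table arises whether one subject is positive three times (1/6 = 17%) or three subjects once each (3/6 = 50%), and it does not show whether they were already positive at Baseline. The listing resolves this only by hand.

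**3. Number of samples affected**

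Post-dose urinalyses per subject are 3 for each Part A dosing period (Days 2, 3 and 7; Appendices 1a and 1b) and 4 in Part B (Days 2, 4, 8 and 7 days after the last dosing day; Appendix 2). Planned numbers come from protocol 4.1 and 5.1.

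- A1 to A5: 40 × 3 = 120
- A6: 8 × 3 = 24
- A7: 6 × 2 periods × 3 = 36
- Part B: 16 × 4 = 64

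Total with A6 and A7 both full: 120 + 24 + 36 + 64 = **244**. With A6 only: 244 − 36 = **208**. With A7 only: 244 − 24 = **220**.

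Day 1 samples are taken as predose. Appendices 1a and 1b say so for Part A; for Part B it is an assumption. The counts include placebo subjects: at 244, these supply 10 × 3 + 2 × 3 + 4 × 4 = 52, leaving 192 from subjects on ABI-4334.

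**The case against.** The strongest opposing case is that nothing is hidden and little is lost. Much of it stands.

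- **Hematuria is not wholly ungradable.** A reader might infer that no scheduled sample can yield any hematuria grade. The row does not support that: visibly bloody urine or an indicated intervention meets Grade 3, and Grade 4 is clinical.
- **Positives are reported.** SAP 5.2.4 does count subjects at each visit, and the listing shows each subject's sequence in cohorts of 6 or 8. What is missing is only the within-subject summary.
- **No false reassurance from an empty row.** A reader might fear that an unmeasured test would be displayed as zero cases. SAP 5.2.1 restricts grading to relevant tests, and SAP 5.2.1.2 uses subjects evaluated for the specific test as the denominator. A test never done has a zero denominator. Appendix 4 is a general scale with other rows that Table 2 does not measure, such as troponin, magnesium and LDL, so an unmeasured row is not in itself an error.
- **Follow-up is possible.** Protocol 8.5 and Appendix 3 allow unscheduled urinalysis and unlisted tests at the investigator's discretion, clinically significant abnormalities become AEs, and the DRC may add assessments. These routes exist, but none is triggered by a positive result.
- **A dipstick positive must not be called hematuria.** This is correct and limits the remedy.

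What remains is that occult blood is measured, yet the row meant to grade urinary blood cannot use it. The SAP already meets a similar problem elsewhere. Direct bilirubin has no Grade 1 or 2 in Appendix 4, and its Grades 3 and 4 require clinical signs or consequences. SAP 5.2.2 therefore gives it a separate treatment-emergent definition with the highest value counted per subject. Occult blood has no such rule.

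**Conclusion.** The mismatch holds in a limited form. Hematuria Grades 1 and 2, and Grade 3 by casts, cannot be assigned from any planned urine sample, and a new positive occult blood result is displayed by visit and listed but never counted per subject as treatment-emergent. Between 208 and 244 post-dose urinalyses are affected at full enrolment, depending on the food-effect cohorts. The top figure needs A6 and A7 both full, although A7 is opened only if too few subjects return for A6. How many samples will be positive is unknown, and only those matter.

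The conclusion assumes that the laboratory reports what Table 2 lists and nothing more. If it routinely reports microscopy, the grades become reachable, but the plan should then say so. The documents do not support a claim that urinary blood goes unreported. The practical weight is modest: one laboratory item in a study with no formal inference, worth correcting because the correction is cheap.

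**What to change.** 1. **SAP 5.2.2 and 5.2.4.** Add, by treatment and cohort, a subject-level shift of occult blood from Baseline to the worst post-Baseline category, using the Baselines in SAP 3.5.4 (by period in Cohort A7). Label it as ungraded occult blood, not hematuria, so that it respects the Appendix 4 exclusion. Mark samples believed to be menstrual; the documents do not show whether the eCRF records this, so the source of the mark should be stated. This parallels the existing direct bilirubin summary.

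2. **Reconcile Table 2 with Appendix 4.** Either list reflex microscopy on the same urine sample when occult blood is positive, so that the grade can be assigned, or state that hematuria Grades 1 and 2 are not assessed in this study.

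**Cost.** The first item is one extra table, with no new samples, and can be made before the SAP is finalized. Reflex microscopy changes Table 2 and adds a small laboratory charge on positive samples only. The downside is a few extra low-grade findings to review. The alternative statement costs one sentence but leaves microscopic hematuria ungraded.
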